6.5 CONTROL LENS IMPLANTATION

The commercially available, posterior chamber, non-accommodating monofocal IOL of the investigators choice will be implanted on Day 0 of the study. A clear corneal incision will be made using the surgeon's standard incision size, instrumentation and technique. All instruments and procedures used will be identical to those routinely used for phacoemulsification by each individual investigator.

6.6 EXAMINATION SCHEDULE

Subjects who agree to participate in the study will return for the listed follow-up examinations for each study eye:

Evaluation	RxSight LAL	- Control
Preoperative	Day -60 to Day -1	Day -60 to Day -1
Operative	Day 0, day of surgery	Day 0, day of surgery
Postop Day 1	Days 1 to 2 postop	Days 1 to 2 postop
Postop Week 1	Days 7 to 14 postop	Days 7 to 14 postop
Postop Week 3	Days 17 to 24 postop: Adjustment #1	Days 17 to 24 postop
Adjustment #2, if needed	3 to 7 days post Adjustment #1	
Adjustment #3, if needed	3 to 7 days post Adjustment #2	
Lock-in #1	3 to 7 days post final adjustment	
Lock-in #2, if needed	3 to 7 days post lock- in #1	
Postop Months 1-2	7 to 14 days post final lock-in visit	Days 30 to 60 postop
Postop Month 6	Days 120 to 180 postop	Days 120 to 180 postop
Postop Month 12, if needed	Days 330 to 420 postop	And the state of t

A Postop Month 12 visit will be conducted if a subject is diagnosed with UV retinal damage to confirm resolution or document sequelae, if any.

Unscheduled visits falling outside the designated ranges for scheduled visits will be considered "interim" visits for data recording purposes and a report form will be completed.

6.7 CLINICAL PARAMETERS

The following study parameters will be assessed as specified in Table 1 for the RxSight LAL and Table 2 for the Control IOL. Assessments will be performed using the techniques described in and in the order presented here and in Table 1.

- 1. Demographics
- 2. Daily Life Erythropsia Questionnaire (DLEQ) (RxSight LAL only)
- 3. Ocular history
- 4. History of Medications
- 5. Corneal Keratometry
- 6. Specular Microscopy (substudy)
- 7. Uncorrected distance visual acuity (UCDVA)
- 8. Manifest Refraction
- 9. Best corrected distance visual acuity (BCDVA)
- 10. In-office Erythropsia Assessment (RxSight LAL only)
- 11. City University Color Test (RxSight LAL only)
- 12
- 13. Intraocular pressure
- 14. Slit Lamp Examination
- 15. Fundus Exam
- 16. Fundus Photos
- 18. Dilated pupil diameter
- 20. Adverse Events

Table 1. RxSight LAL Schedule of Visits and Clinical Parameters

Table 1. RxSight LAL Schedule of Visits and Clinical Parameters													
Visits	Preop	Орегайче	Postop Day 1	Postop Week 1	Postop Week 3	Adjustment #2 (If needed)	Adjustment #3 (if needed)	Lock-in #1	Lock-in#2 (if nædeil)	Postop Months 1-2	Postop Mouth 6	Postop Month 12 (if needed)	Unscheduled Visit
Demographics	Х												
Daily Life Brythropsia Questionnaire (DLEQ)					х	X	х	х	х	X ⁴	х	Х	X
Ocular History	х												
History of Medications	Х	Х	X	Х	х	X.	х	Х	х	X	х	X	Х
Corneal Keratometry	х												
Specular Microscopy ³	Х				х						x		
Uncorrected distance visual actity (UCDVA)	х		х	х	М	х	Х	х	х	X	М	х	х
Manifest Refraction	х			х	M	X	х	х	х	х	M	Х	
Best corrected Visual Acuity Distance (BCDVA)	:x			X.	M	· x ·	X	х	х	х	М	х	
In-office Erythropsia Assessment					X.	Х	x	x	x	X	x	X	х
City University Color Test					Х	X	X	х	Х	Х	х	х	X ⁵
					х	X1	X1	χ¹	$\mathbf{X_{l}}$	Χı	Xi	X ¹	
Intraocular Pressure	X		х	х	х	х	х	X	х	х	X	Х	
Slit Lamp Exam	X		X	х	X	х	х	х	Х	X.	х	x	х
Fuidus Exam	X				Х	х	х	Х	X		x	х	
Fundus Photos	х				Х	х	Х	х	х		X	Х	
					х	×	х	х	x	x	x	x	
Dilated Pupil Diameter	x				х	х	х	x	х				
						χı	X ¹	Xi	X	Xi	$\mathbf{X}_{\hat{\mathbf{I}}}$	χi	
Adverse Events		х	Х	х	х	х	x	х	х	X	X	X	Х

are only required if the events described in Section 6.4.2.2 of the protocol occur.

"Tests indicated with an "X" must be performed at each unscheduled visit. Other tests may be conducted based on the investigator's assessment of the subject.

Specular microscopy will be performed on a subgroup of approximately 300 eyes including a minimum of 192 LAL eyes and 96 Control eyes.

If the subject reports any degree of crythropsia at the Postop Month 1-2 visit OR at any interim visit after the Postop Month 1-2 visit and <90 days after surgery, the subject will be contacted between 90-120 days after surgery and asked to complete the Daily Life Erythropsia Questionnaire.

M Measurements will be conducted by a masked observer who will not be aware of which lens has been implanted in the eye. The masked observer should not

have access to the subject's medical and/or study records.

⁵Must be performed at any unscheduled visit which occurs at 3-months or later.

Table 2. Control IOL Schedule of Visits and Clinical Parameters

1 abie 2. Control i	IOL Schedule of Visits and C				unican i	Parameters			
Visits	dosaa	Орегайче	Postop Day I	Postop Week 1	Postop Weck 3	Postop Months 1-2	Postop Month 6	Unscheduled Visit	
Demographics	х								
Ocular History	х								
History of Medications	x	X	Х	X	X	х	Х	х	
Corneal Keratometry	x								
Specular Microscopy (substudy) ²	х				X		Х		
Uncorrected distance visual acuity (UCDVA)	х		X.	X	М	x	М	-x-	
Manifest Refraction	Х			х	M	x	М		
Best corrected Visual Acuity Distance (BCDVA)	х			x	М	х	M		
Intraocular pressure	X		Х	Х	Х	X	х		
Slit Lamp Exam	Х		X	х	Х	х	Х	х	
Fundus Exam	х				Х		х		
Fundus Photos	х				X		x		
Dilated Pupil Diameter	x				х				
Adverse Events		х	Х	X	Х	Х	х	x	

Tests indicated with an "X" must be performed at each unscheduled visit. Other tests may be conducted based on the investigator's assessment of the subject. Specular microscopy will be performed on a subgroup of approximately 300 eyes including a minimum of 192 LAL eyes and 96 Control eyes, Measurements will be conducted by a masked observer who will not be aware of which lens has been implanted in the eye. The masked observer should not have access to the subject's medical and/or study records.

6.8 DATA REPORTING

Electronic data capture (EDC) will be utilized for this study. Case report forms (CRFs) will be provided by the sponsor for each eye enrolled in the study. In order to facilitate data entry, the CRFs coincide with the data entry pages in the EDC system. The appropriate CRFs will be completed and initialed or signed where indicated at each examination. All CRFs will be completed in a legible manner in black/blue ink.

Any corrections to the CRFs will be made by drawing a single line through the incorrect entry, recording the correct information, and initialing and dating the change. The study CRFs and data entered in the EDC system will be reviewed by the Study Monitor.

All clinical data generated in the study will be submitted to the RxSight Clinical Affairs Department or designated CRO for quality assurance review and statistical analysis. All CRFs and data entered into the EDC system will be reviewed for completeness and evident recording errors will be rectified by contact with the appropriate clinical site. Computerized data checks will be used to identify unusual data entries for verification prior to statistical analysis.

To minimize the amount of missing data, investigators will be trained on the deleterious effect that missing data have on trial integrity and credibility and that missing data could diminish the scientific value of all subjects' altruistic contributions.

6.9 STUDY COMPLETION PROCEDURES

An End of Study Form must be completed for all subjects enrolled in the study upon subject completion, withdrawal or discontinuation.

6.9.1 SUBJECT COMPLETION

Subjects are considered to have completed the study if they have completed the Postop Month 6 examination unless the subject is diagnosed with retinal phototoxicity. In that case, a Month 12 examination will be conducted for the RxSight LAL group only to confirm resolution or document sequelae, if any.

Subjects with ocular serious adverse events or adverse device effects that are unresolved at study exit should continue to be followed until resolution of the event or until they are stable per the investigator's evaluation.

6.9.2 SUBJECT WITHDRAWAL PRIOR TO IMPLANTATION

Subjects may be withdrawn from the study prior to implantation if they do not meet all inclusion/exclusion criteria (screen failures) or decide not to participate in the study.

6.9.3 SUBJECT WITHDRAWAL DUE TO INTRAOPERATIVE COMPLICATIONS PRIOR TO IMPLANTATION

Subjects that meet all inclusion/exclusion criteria but do not undergo implantation of the RxSight LAL due to intraoperative complications prior to introduction of the RxSight LAL will be followed to resolution of any adverse events and then exited from the study.

6.9.4 SUBJECT DISCONTINUATION AFTER IMPLANTATION

After implantation, subjects may not be withdrawn from the study unless the study lens has been explanted. In the case of an explant, the investigator should continue follow-up for a period that ensures no adverse consequences have resulted. When possible, all necessary clinical assessments will be performed prior to the Subject exiting the study even if the assessment was not scheduled at that particular visit.

Subjects may be discontinued from the study only when the study lens has been explanted or subject has deceased. The reason for discontinuation will be recorded on the appropriate study worksheet. Subjects who are discontinued from the study will still be a part of the study analyses up until the point they are exited.

6.9.5 LOST TO FOLLOW-UP

Subjects for which the final post-operative case report form is overdue and who refuse to be followed, or have difficulty being followed, or cannot be contacted despite extensive written and telephone follow-ups to determine the final clinical outcome, will be considered lost to follow-up. Sites must make a minimum of three documented attempts via telephone, email, or regular mail to contact the subject. If the subject does not reply to any of these attempts, the site must send a letter by certified mail (with a request for notification of receipt of delivery) to the subject. If a subject is non-responsive to these follow-up attempts, the subject will be considered to be lost to follow-up.

7 STATISTICAL METHODS

7.1 SAMPLE SIZE CALCULATION

The sample size calculations for the post-approval study are based on the two safety endpoints and their corresponding statistical hypotheses described below.

[figure not shown]
7.1.1 ENDOTHELIAL CELL DENSITY (ECD)

The endothelial cell loss (ECL) at 6 months after the cataract surgery will be compared between the LAL and Control groups.

7.1.2 UV RETINAL DAMAGE NOT DETECTABLE THROUGH ROUTINE CLINICAL EXAMINATIONS

7.2 GENERAL CONSIDERATION—

The statistical analysis of the data will be performed using SAS version 9.3 or higher or another industry standard statistical software package. Continuous variables will be summarized using descriptive statistics, specifically the mean, median, standard deviation, minimum and maximum. Categorical variables will be summarized by frequencies and percentages. Safety analyses will be performed on eyes in which IOL implants are attempted.

A detailed statistical analysis plan (SAP) will be developed and finalized prior to the locking of the database for this study.

7.3 BASELINE CHARACTERISTICS

Baseline characteristics (such as age, gender, race, and pre-operative pathology) will be summarized descriptively by means and standard deviations or by counts and percentages, as appropriate. They will also be stratified by the study site in order to assess the similarity of these baseline characteristics among the study sites.

7.4 POPULATIONS FOR ANALYSIS

7.4.1 SAFETY POPULATION

The safety population consists of any subject who has signed the informed consent and has the procedure attempted which is defined as the point at which the lens makes contact with the eye. This population will be used for the safety. No imputation will be performed.

³ Conover, W.J. (1980). Practical Nonparametric Statistics 2 ed. J. Wiley, New York

7.4.2 ENDOTHELIAL CELL POPULATION

[figure not shown]
The endothelial cell population consists of members of the safety population who are entered in the endothelial cell subgroup and have specular microscopy images taken at the preoperative examination.

7.4.3 EFFECTIVENESS POPULATION

The effectiveness population consists of members of the safety population who are implanted with the randomized intraocular lens and have the 6-month manifest refraction data.

7.5 EFFECTIVENESS ANALYSES

The following effectiveness outcomes will be summarized descriptively based on the observed data of the effectiveness population for the RxSight LAL and Control eyes separately.

[figure not shown]

7.6 SAFETY PARAMETERS

[figure not shown]
All data analyses will be based on the observed data and actual lens implanted. No imputation will be performed for the missing data.

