6 STUDY POPULATION

The Phase B study will include 500 subjects who will be randomized 2:1 to receive either an RxSight LAL or a monofocal control IOL.

Subjects should be screened for eligibility and only eyes meeting all inclusion and none of the exclusion criteria will qualify for implantation.

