6.3 SUBJECT ENTRY

Patients who require cataract extraction and intraocular lens implantation will be screened for eligibility. If it is determined that the patient may be eligible to participate, study staff will explain the study purpose, procedures, risk/benefits and subject responsibilities to the potential participant. Written informed consent will be obtained prior to any study specific testing. The patient is enrolled upon signing the informed consent. The subject will sign and date the informed consent form in the presence of the person conducting the consent process. The investigator and/or the person conducting the consent process will also sign and date the consent form. The preoperative examination will be performed no more than 60 days prior to surgery. If the 60-day time period elapses, it is acceptable for patients to be re-screened by undergoing a complete preoperative examination.

Only subjects meeting all inclusion/exclusion criteria will be implanted. Those subjects who do not meet the inclusion/exclusion requirements will be considered screen failures. Subjects will continue to be enrolled until 500 subjects have been randomized and undergone implantation with the RxSight LAL or a monofocal IOL. If surgical complications occur and no LAL is implanted, the subject is exited from the study. Unique identification numbers will be assigned to each subject. The randomization schedules for each site will be prepared in advance and only the study statistician will have access to the randomization schedule. Prior to the surgical procedure, study site personnel will enter the subject's study ID into the study's EDC system and the treatment assignment (RxSight LAL or Control IOL) will be generated. Documentation of the randomization assignment for each subject will be maintained in the subject's file and in the EDC system.

The implant lens power for the RxSight LAL and the Control IOL will be calculated based upon the ocular biometry data and a standard IOL power calculation formula with the IOL closest to the post-surgical refractive target selected in an unbiased manner.

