7.6.3 Additional Safety Analyses

The following safety outcomes will be summarized descriptively based on the observed data and actual lens implanted. Results will be presented for all the RxSight LAL eyes and the Control group eyes. The 95% confidence intervals for means or percentage may be presented, as appropriate.

Adverse Events

Number and percent of study eyes will be summarized for each reported ocular AE at the operative visit and each postoperative visit for the LAL group and Control group separately. Serious ocular AEs and the non-ocular serious AEs will be summarized in the same manner. Additionally, for each of the device related AE reported during the study, the number and

percent of study eyes reported with the event will be presented. The ocular adverse events will be listed for eyes, if applicable, with IOL implantation attempted but without implantation. Ocular adverse events will be reported separately for the fellow eye.

BCDVA

BCDVA will be presented with the number and percent of eyes who fall into each category of BCDVA at each visit (e.g. 20/20 or better, 20/25 or better, 20/32 or better, etc.). The mean and standard deviation (SD) of BCDVA letter score will also be calculated for each visit. Change in BCDVA from Postop Week 3 or from Preoperative will be presented at each visit as categorical outcomes of "Increase in 15 letters or more", "Increase in 10-14 letters", "Increase in 5-9 letters", "No change", "Decrease in 5-9 letters", "Decrease in 10-14 letters", and "Decrease in 15 letters or more The mean and SD of the change from Postop Week 3 or Preoperative will also be presented. Similarly, the mean change from the prior visit to the next visit will also be summarized in the same manner.

In-Office Erythropsia Assessment (RxSight LAL only)

The number and percent of eyes in each outcome of erythropsia assessment (0- white, 1-pink, or 2- red) will be presented. In addition, the number and percent of eyes with increases in the level of erythropsia from the Postop Week 3 visit will be presented.

Daily Life Erythropsia Questionnaire (RxSight LAL only)

Results of the Daily Life Erythropsia Questionnaire will be summarized descriptively at each visit the questionnaire is completed.

City University Color Test (RxSight LAL only)

[figure not shown]
Results of the City University Color Test will be reported as the number and percent of eyes that have tritan findings >1 on Part Two of the test.

Slit Lamp Examinations

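### An eye in which LAL insertion fails after lens contact is in the safety population but, as written, falls outside the LAL operative adverse event rate

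*Combined protocol and SAP*

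**What the plan says.** Two sections define the safety set by attempt. Section 7.2 says "Safety analyses will be performed on eyes in which IOL implants are attempted". Section 7.4.1 admits a consented subject who "has the procedure attempted which is defined as the point at which the lens makes contact with the eye".

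Two sections set the grouping by outcome of surgery. Section 7.6 says "All data analyses will be based on the observed data and actual lens implanted". Section 7.6.3, which contains the adverse event tables, says "The following safety outcomes will be summarized descriptively based on the observed data and actual lens implanted" and presents the events for the LAL and Control groups separately.

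Section 7.6.3 foresees eyes that fall between the two: "The ocular adverse events will be listed for eyes, if applicable, with IOL implantation attempted but without implantation". No percentage or denominator is attached to that listing.

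On disposition, section 6.3 says "If surgical complications occur and no LAL is implanted, the subject is exited from the study". Section 6.9.3 is narrower: otherwise eligible subjects who "do not undergo implantation of the RxSight LAL due to intraoperative complications prior to introduction of the RxSight LAL will be followed" until adverse events resolve, and then exited. Section 6.3 also keeps enrolment open until 500 subjects have been both randomised and implanted.

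**The concern.** Consider a LAL that touches the eye, cannot be placed satisfactorily and is removed during the same operation. The eye is in the safety population by definition. If it leaves surgery without a LAL, grouping by the implanted lens gives it no place in the LAL column. Its ocular events go to a listing. A non-ocular serious event in that subject has no stated place at all, because the listing covers ocular events only.

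Failed insertions are where harm from the insertion step would be expected to concentrate. Leaving them out makes the LAL operative rate look better whenever those eyes have events more often than the remaining LAL eyes. Because enrolment continues until 500 are implanted, the final LAL denominator would not reveal the loss. This matters in a post-approval study whose objective is safety (section 3) and which names rates of all types of adverse events in LAL eyes as a key safety parameter (section 5.2).

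**Working it through.** **No stated figure to reproduce.** The plan gives no expected number of failed insertions and no expected operative event rate. The check is a reading of the rules, then an illustration of size.

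**Step 1: follow one eye through the rules.** The LAL contacts the eye, is removed, and no LAL is left in.

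| Question | Section | Result |
|---|---|---|
| In the safety population? | 7.2, 7.4.1 | Yes: contact has occurred |
| Covered by the rule on complications before LAL introduction? | 6.9.3 | No: the lens has already been introduced |
| Continues in the study? | 6.3 | No, if the failure counts as a surgical complication: exited |
| In the LAL adverse event percentages? | 7.6, 7.6.3 | No: the LAL is not the lens implanted |
| Reported elsewhere? | 7.6.3 | Ocular events in a listing only |
| Class if another lens is placed? | none visible | Not stated |

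**Step 2: inputs for size.**
- Section 6: "The Phase B study will include 500 subjects who will be randomized 2:1". This gives 500 × 2/3 ≈ 333 LAL eyes and 500 × 1/3 ≈ 167 Control eyes.
- k = number of LAL eyes that fail after contact, in addition to the 333 implanted. Assumed range 1 to 5.
- Each such eye has an adverse event (assumption).

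**Step 3: contribution missing from the LAL rate**, k / (333 + k), when no other LAL eye has an event:

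| k | Counted as attempted | Grouped by implanted lens | Understatement |
|---|---|---|---|
| 1 | 1/334 = 0.30% | 0/333 = 0% | 0.3 points |
| 3 | 3/336 = 0.89% | 0/333 = 0% | 0.9 points |
| 5 | 5/338 = 1.48% | 0/333 = 0% | 1.5 points |

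**Step 4: does a background of other events change this?** With a events among the 333 implanted eyes, the understatement is (a + k)/(333 + k) − a/333 = [k/(333 + k)] × (1 − a/333). Taking a = 5 for illustration, the implanted-only rate is 5/333 = 1.50%. Counting attempted eyes gives 6/334 = 1.80% (k = 1), 8/336 = 2.38% (k = 3) and 10/338 = 2.96% (k = 5). The gaps are again about 0.3, 0.9 and 1.5 points.

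**Step 5: which outcomes are touched?** An exited eye has no month 6 specular microscopy, and an eye without a LAL receives no light treatment. Neither the month 6 cell-loss comparison nor the UV retinal damage rate changes materially. The effect lies in operative and early adverse events.

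**The case against.** The best defence is that the two sets of sections answer different questions: 7.2 and 7.4.1 say who is in the set, and 7.6 and 7.6.3 say how members are grouped. As-treated grouping within an attempt-based set is common, and the leftover eyes are disclosed in a listing. This stands to the extent that the sections are not in outright contradiction and the ocular events are not hidden. It does not restore the eyes to a rate: a listing has no denominator and no confidence interval.

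A reader might go further and infer that a failed LAL eye given a monofocal lens would be counted as Control, moving LAL harm into the comparator. At k = 3 that would add 3/170 = 1.8 points to Control on top of the 0.9 lost from LAL, a shift of about 2.7 points. The documents do not support this. No section says such an eye joins Control, the exit rule in 6.3 weighs against it, and the listing treats uncompleted implantations separately. What remains is only that its classification is not stated.

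Three further points have force:
- Section 6.9.4 keeps subjects whose lens is explanted in the analyses until exit. A LAL placed and removed in one operation might be read as implanted and then explanted, and so stay with LAL. The boundary is undefined, which is itself a reason to state the rule.
- The adverse event summaries are descriptive, and the same grouping would also drop a failed Control insertion from the Control rate. The firm claim therefore concerns the LAL rate, not a biased test between arms.
- Parts of 7.6 are not visible, and 7.2 promises a detailed SAP before database lock. A classification rule may exist there; its absence from the whole plan cannot be asserted.

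**Conclusion.** The concern holds in a limited form. Under the visible rules, an eye in which LAL insertion fails after contact is in the safety population but outside the LAL operative adverse event rate, and the class of an eye given a different lens is left open. The understatement is about 0.3 to 1.5 percentage points for 1 to 5 such eyes. That rests on an assumed count, on every such eye having an event, and on about 333 implanted LAL eyes. With no failed insertions there is no effect, and with fewer events among them it is smaller. The matter is worth correcting because the stated rule, applied as written, tends to favour the device on a named safety parameter, and the correction is cheap. It gives no reason to doubt the month 6 co-primary endpoints.

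**What to change.** Limit the change to the Adverse Events paragraph of section 7.6.3, and carry it into the detailed SAP before database lock:

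- Tabulate ocular, serious ocular, non-ocular serious and device-related adverse events by the lens first attempted, defined as the first study lens to contact the eye. Apart from allocation errors this equals the randomised arm.
- Count all attempted eyes in that arm's numerator and denominator, including an eye that ends surgery with a different lens or none.
- Keep the listing of attempted but uncompleted implantations, and show the as-implanted table alongside.
- Add to 7.6 a cross-reference to this exception.

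Leave section 7.6.4 (refractive and acuity outcomes) unchanged, and keep the UV-damage, erythropsia and colour-test analyses on eyes actually implanted with the LAL. Adding eyes that had no light treatment to those denominators would dilute the rates of interest.

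The cost is a few sentences, one grouping variable and one extra table. The only downside is that the LAL operative adverse event rate may look slightly less favourable.
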